6.1.9 Training of Centres in the Behavioural Support Component

All research staff with potential direct contact with participants at any time point, including fitness assessments, exercise program prescription, exercise supervision, and phone or in-person contact, will complete a web based training (approximately 45-60 minutes) on behavioural support. The training includes an on-line exam that everyone must score at least 80% correct responses. The centres are responsible for ensuring that all personnel are trained and must keep records of training compliance. This training will need to be completed before any exercise testing or supervised exercise sessions start.

7.0 PSYCHO-SOCIAL SUPPORT (Supervised Exercise and Self-directed Exercise Groups)

Psycho-social support will be provided for all participants in the study. Participants will be provided with a two-or three-page newsletter each cycle either via e-mail or paper mail. The newsletters will include information on a variety of topics relevant to prostate cancer survivors. Participants will be sent one topic per cycle. Content for the psycho-social support newsletters will include:

- Newsletter 1* “Staying Healthy – Lifestyle Behaviours”
- Newsletter 2* “Goal Setting”
- Newsletter 3* “Managing Fatigue”
- Newsletter 4* “Bone Health”
- Newsletter 5* “Side Effects of Treatment”
- Newsletter 6* “Maintenance of Health Behaviors”
- Newsletter 7* “Depression”
- Newsletter 8* “Securing Social Support”
- Newsletter 9* “Pain Management”
- Newsletter 10* “Sexual Intimacy”
- Newsletter 11* “Cognitive Changes”
- Newsletter 12* “Gaining Control”
- Newsletter 13* “INTERVAL: Your Participation”
- Newsletter 14* “Hormone Therapy”
- Newsletter 15* “Sweets and Sweeteners”
- Newsletter 16* “Maintaining Control”
- Newsletter 17* “Communication”
- Newsletter 18* “Optimize your Sleep”
- Newsletter 19* “Managing Stress”
- Newsletter 20* “Nutrition & Fatigue”
- Newsletter 21* “Plant-Based Diets”
- Newsletter 22* “Cognitive Changes: Memory”
- Newsletter 23* “Optimize Your Quality of Life”
- Newsletter 24* “Beyond the INTERVAL Study”

8.0 METABOLIC RESEARCH STUDIES

8.1 Rationale

Understanding how exercise affects prostate cancer biology and clinical outcomes among men with prostate cancer requires in-depth interrogation of candidate biological systems and pathways. Several potential

mechanisms (outlined in Section 1.2) have been proposed to explain the effect of exercise on disease progression, the incidence and progression of comorbidities, treatment-related side effects, and overall survival among men with prostate cancer. Based on the prevalence of metabolic and endocrine dysfunction in men with MCRPC, the established benefit of high intensity aerobic and resistance exercise for metabolic health in various populations, and the highly-integrated regulation of inflammation, energy metabolism, and endocrine systems,⁴⁸ we propose to focus the initial metabolic research studies on three candidate pathways: systemic inflammation, insulin/glucose metabolism, and androgen biosynthesis.

8.2 Hypotheses

- Men randomised to exercise will have a smaller increase in systemic inflammation over time compared to men randomised to the control group, as measured by circulating IL1 β , IL2, IL6, TNF α adiponectin, and C-reactive protein (CRP) levels.
- Men randomised to exercise will have improved insulin sensitivity over time as seen by lower circulating insulin levels and improved glucose tolerance compared to men randomised to the control group, as measured by the homeostasis model assessment of insulin resistance (HOMA-IR) and circulating levels of insulin, glucose, C-peptide, HbA1c, and IGF-1.
- Baseline levels of testosterone, dihydrotestosterone (DHT), androstenedione, dehydroepiandrosterone (DHEA), 17-hydroxyprogesterone, 17-hydroxypregnenolone and progesterone are affected by exercise
- High levels of systemic inflammation, insulin resistance, and low androgens at baseline and over time will be associated with shorter OS among men with mCRPC.
- Changes in inflammatory biomarkers, insulin/glucose metabolism, and androgens will mediate the hypothesized relation between exercise and OS among men with mCRPC.

8.3 Blood Collection for Metabolic Studies

Fasting Blood (26 ml) will be taken for the metabolic research analyses at baseline and Cycles 6, 12 and 24 from all consenting patients in both Arms A and B. Blood will be processed to plasma, buffy coat and serum. Fasting blood will be taken in the morning following an overnight fast of at least 12-hours where there was no food intake and a minimum of 48 hours since the last vigorous exercise session. The time of the blood draw and the last meal should be recorded. Blood draws can occur on the same day as the exercise assessment, prior to commencement of the assessments.

8.3.1 Plasma/Buffy Coat

20 ml of fasting blood will be collected in EDTA tubes and processed to plasma. Blood samples will be labelled with the patient's registration number and processed to plasma according to Research Blood Collection and Processing SOP (see SOM: [Appendix 17](#)) where the cellular components (buffy coat) will be retained after collection of the plasma. Aliquoted plasma and buffy coat will be stored at -80°C until batch transport. Blood needs to be processed within **one hour** of sampling.

8.3.2 Serum

6 ml of fasting blood will be collected in plain non-heparinised tubes and processed to serum. Blood samples will be labelled with the patient's ID number and processed to serum according to Research Blood Collection and Processing SOP (see SOM: [Appendix 17](#)). Serum will be collected in a manner which ensures suitability of the sample for downstream analysis of nucleic acids and protein factors. Aliquoted serum will be stored at -80°C until batch transport. Blood needs to be processed to serum within **2 hours** of sampling.

8.4 Biorepository

A secondary objective of the Metabolic Research Studies is to build a biorepository to enable future molecular and protein studies to thoroughly interrogate the effect of exercise among men with MCRPC at the systemic, muscular, and prostate-specific level. Serum, plasma and buffy coat will form part of this biorepository in addition to the samples discussed briefly below that will be collected from consenting patients.

8.4.1 Formalin Fixed Paraffin Embedded Tissue

Permission to access archived diagnostic, radical prostatectomy or bone marrow and metastatic biopsy formalin fixed paraffin embedded (FFPE) tissue blocks and slides will be requested from all patients in the consent form. The FFPE blocks will be collected at a later time point. Inability to access archived FFPE tissue will not exclude patients from participation in this study. All slides and blocks following cutting will be returned to their original pathology department.

8.4.2. Urine

Morning first void urine will be collected from all patients in the Arms A and B at baseline and within 7 days on or after Day 1 of Cycles 6, 12, and 24, and a minimum of 48 hours since the last vigorous exercise session. Patients will be provided with a sterile container by the research team. The patient will be asked to record the time of void. Urine will be processed according to Urine Collection and Processing SOP (SOM: [Appendix 18](#)). Urine will be collected in a manner which ensures suitability of the sample for downstream analysis of nucleic acids and protein factors. Aliquots will be stored at -80°C.

8.5 Storage and Transport of Samples

- Plasma, serum, buffy coat and urine will be stored locally at sites at -80°C until batch transport on dry ice to designated regional retention centres (SOM: [Appendix 19](#))

8.6 Duration and retention of samples

All samples will be stored indefinitely at their final storage site as detailed in the SOM: [Appendix 19](#). Access will be permitted only to individuals/groups who have received permission from the GAP4 steering committee. Investigators will request access to samples by petition to the GAP4 steering committee. Investigators will be required to provide specific hypotheses relevant to the goal of elucidating the role of exercise in prostate cancer patients and funding for any proposed biomarker assays.

9.0 OFF-TREATMENT

Subjects will remain on treatment until the Month 24 Off Study visit; however, a patient may be discontinued from study intervention at any time if the patient, the Investigator, or the DSMB feels that it is not in the patient's best interest to continue on study. If a patient must be discontinued, this will not result in automatic withdrawal of the patient from the study.

The following is a list of possible reasons for early discontinuation of study interventions:

- An adverse event that cannot be adequately managed with intervention modifications
- Protocol violation requiring discontinuation of study intervention
- Lost to follow-up
- Patient withdrawal of consent
- DSMB request for early termination of study
- Progression is NOT a reason for study termination

All patients discontinuing study interventions will complete an Off Study visit (if able), and enter into the follow-up period.

If a patient is lost to follow-up, every reasonable effort must be made by the study site personnel to contact the patient and determine the reason for discontinuation/withdrawal. The measures taken to contact the patient must be documented. When a subject withdraws before completing the study, the reason for withdrawal is to be documented in the CRF and in the source document. Subjects who withdraw will not be replaced.

Note: PROGRESSION: Every effort should be made to keep patients who progress on study for the duration of the trial period.

10.0 PRIMARY ENDPOINT CRITERIA FOR OVERALL SURVIVAL

Patients will be followed for death a minimum of 36 months after randomisation. Overall survival will be measured from the time of randomisation until death. Medical records and death certificates will be reviewed every 6 months to obtain survival status. Country-specific mortality status databases will also be searched annually; cause of death will be determined through review of medical and death records. Patients will be contacted once a year, and follow up with next of kin then alternate contact, if needed, if we do not hear from them.

11.0 SECONDARY ENDPOINTS

11.1 Disease progression

Data on disease progression will be obtained through review of patient medical records each cycle. Progression will be determined by the treating physician, and may include any of the following, based on PCWG-3 and RECIST 1.1 criteria:

- Bone scan: Appearance of ≥ 2 new lesions on bone scan, if bone scan >12 weeks after randomisation
- CT/MRI: $\geq 20\%$ increase in the sum of diameters, taking the reference as the smallest sum on study. In addition to the relative increase by 20%, the sum must also demonstrate an absolute increase >5 mm. OR The appearance of one or more new lesions. OR Unequivocal progression of baseline unmeasurable lesions (see further details below). If the patient has measurable disease, there must be overall worsening in non-measurable disease such that the overall tumour burden has increased substantially. The designation of disease progression solely on the basis of change in non-measurable disease in the face of stable disease or partial response of the measurable disease is extremely rare.
- Development of an indication for initiating a therapy for MCRPC after randomisation, including, but not limited to, abiraterone, enzalutamide, chemotherapy, or radiation therapy.
- Symptomatic-skeletal related event (SSE).

Progression free survival will be measured from randomisation until the first of the following: first CT or bone scan documenting disease progression, initiation of a new therapy for MCRPC (clinical progression), or first occurrence of a SSE.

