APPENDIX 34: COST OF PARTICIPATION QUESTIONNAIRE (4 versions: 2 for each group, SE and SDE)

1.0 INTRODUCTION

1.1 Exercise as Non-Pharmacologic Adjuvant Therapy for Prostate Cancer

Identifying and evaluating low-toxicity adjuvant interventions that can be combined with standard therapy to improve outcomes for men with prostate cancer is a high priority and has the potential to have a large impact on the clinical and public health burden of prostate cancer. We summarise briefly below promising observational, pre-clinical, and pilot clinical data that support the hypothesis that exercise improves overall survival and health-related quality-of-life (QOL) among men with advanced prostate cancer:

- Vigorous aerobic exercise after diagnosis was associated with a 60% lower risk of fatal prostate cancer and a 49% lower risk of all-cause mortality among men initially diagnosed with localised disease (Figure 1).²
- Among men diagnosed with incident *advanced* prostate cancer (clinical stage T3 or higher), those who reported ≥ 3 h/wk of non-vigorous activity after diagnosis had a 36% lower risk of death compared to men reporting <1 h/wk (events: 194; HR: 0.64; 95% CI: 0.42, 0.96; p -trend: 0.006) (unpublished, please do not cite/quote; [name] personal communication).
- Loading of bone inhibited growth of metastatic tumours in animal models.³
- Resistance exercise and programs with both resistance and aerobic exercise improved physical function and quality-of-life in men without metastases on androgen deprivation therapy (ADT) for prostate cancer.^{4,5}
- Treatment-related fatigue is a common side effect in men with advanced prostate cancer,^{6,7} and exercise may decrease fatigue and increase adherence to treatment regimens.
- New standard treatments for advanced prostate cancer cause adverse metabolic effects (e.g., weight gain, insulin resistance) that may be avoided or attenuated by exercise.

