3.0 ELIGIBILITY CRITERIA

3.1 Inclusion Criteria

- Patients must be mCRPC. This is defined as adenocarcinoma of the prostate with systemic metastatic disease despite castrate levels of testosterone (<50 ng/dL) due to orchiectomy or LHRH agonist.
 - Patients must have one or more of the following to be considered mCRPC
 - Metastatic Disease Progression: >20% increase in the sum of diameters of measurable lesions from the time of maximal regression or appearance of one or more new lesions.
 - Bone Scan Progression: Appearance of one or more new lesions on bone scan attributable to prostate cancer.
 - PSA Progression: PSA \geq 2 ng/ml that has risen serially on at least two occasions, each at least one week apart (PSA1 < PSA2 < PSA3).
- Castrate levels of testosterone must be maintained while on study. Be on androgen deprivation therapy (ADT) with a GnRH agonist/antagonist or prior bilateral orchiectomy. All patients will be required to be on ADT during the study period or have had a prior bilateral orchiectomy. Men with small cell neuroendocrine tumours or features of small cell disease are not eligible.
- At enrolment, patients must fit into one of the following 4 categories:
 1. Treatment naïve for mCRPC (have not yet started approved therapies for CRPC ie: Abiraterone/Enzalutamide/Apalutamide/Docetaxel; less than 4 weeks on approved therapies is still considered to be treatment naïve)

Or

 2. Receiving Abi/Enza/Apa for mCRPC AND responding or stable (PSA values must be stable or declining after at least 4 weeks since starting Abi/Enza/Apa for mCRPC)

Or

 3. Patients with PSA progression while on Abi/Enza/Apa are eligible as long as they are asymptomatic AND there is no intent on starting chemotherapy within 6 months

Or

 4. Patients treated with Docetaxel as first line therapy for mCRPC who are asymptomatic without ANY evidence of progression

Or

 5. Patients may have progressed following Docetaxel first line and are now receiving treatment with Abi/Enza/Apa. These patients must absolutely be responding or stable (PSA values must be stable or declining after starting Abi/Enza/Apa treatment) and have an expected life expectancy of more than 1 year.
- \geq 4 weeks since any major surgery and fully recovered.
- Halabi Nomogram score <195¹ (Risk Category rated as low or intermediate risk)
- Age \geq 18 years
- Eastern Cooperative Oncology Group (ECOG) performance status 0-1

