4.5 Stratification

Patients will be stratified by study site and treatment status at the time of registration: 1) Patients who are treatment naïve or stable on Abiraterone/Enzalutamide/Apalutamide or 2) Patients who are on/received first line chemo OR progressing on first line Abiraterone/Enzalutamide/Apalutamide. Patients treated with radium-223 will need medical monitoring review for correct stratification placement. Previous and/or concurrent treatment with other anti-cancer therapies is permitted. Patients who have previously received sipuleucel-t, meet study eligibility, and are not on the treatments listed above, are not considered on treatment. Patients

receiving experimental treatment with non-approved drugs at the time of enrolment are not eligible. Patients receiving treatment with combinations of approved drugs are eligible, provided documentation and clearance by the SCC.

Allocation within strata will be carried out using blocked randomisation in random blocks of 2, 4, or 6.

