5.1.5 Concomitant Medications/Therapies

Standard medical treatment as applicable is allowed. Additionally, any therapy initiated after randomisation for the treatment of MCRPC should be preceded by documented clinical evidence of disease progression, a SSE, pain, or other clinical indication. Every medication or treatment taken by the patient during the trial and the reason for its administration must be recorded on the CRF. All concomitant medication and concurrent therapies will be documented from informed consent until 28 days after Cycle 24 (end of intervention): name, indication for administration, and dates of medication or therapy (SOM: [Appendix 11](#)).

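### PFS can be ended by a first-line therapy already indicated or intended at randomisation, because the two statements in Section 11.1 do not agree

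*Combined protocol and SAP*

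**What the plan says.** Section 11.1 of the protocol refers to therapy starts twice. Its list of what may count as progression includes "Development of an indication for initiating a therapy for MCRPC after randomisation, including, but not limited to, abiraterone, enzalutamide, chemotherapy, or radiation therapy". Its closing sentence then defines PFS as running from randomisation to the first of a CT or bone scan showing progression, "initiation of a new therapy for MCRPC (clinical progression), or first occurrence of a SSE". Section 12.5 takes its PFS event from Section 11 and adds no detail on therapy starts.

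Section 3.1 requires every man to show measurable-disease, bone-scan or PSA progression in order to count as mCRPC. Entry category 1 is "Treatment naïve for mCRPC (have not yet started approved therapies for CRPC", with the rider that "less than 4 weeks on approved therapies is still considered to be treatment naïve".

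Section 5.1.5 allows standard treatment and says that mCRPC therapy begun after randomisation "should be preceded by documented clinical evidence of disease progression, a SSE, pain, or other clinical indication".

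Section 4.5 puts "Patients who are treatment naïve or stable on Abiraterone/Enzalutamide/Apalutamide" in one randomisation stratum. Section 12.5 stratifies the PFS log-rank test by treatment status at registration.

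**The concern.** The two statements in Section 11.1 can classify the same man differently. Take an untreated category 1 man whose first-line drug was chosen before consent and begun three weeks after randomisation. Under the list, no indication has developed since randomisation, so he has not progressed. Under the PFS sentence he has an event at three weeks. The progression behind that treatment is the one that made him eligible.

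If such starts are counted, they add early events whose timing reflects treatment plans made before allocation. Exercise cannot have influenced those plans, so the events dilute the comparison and shorten the reported median and yearly PFS rates. PFS is the first-listed secondary objective (Section 2.2). Two analysts following different sentences of Section 11.1 could also report different PFS results from the same data.

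**Working it through.** The plan gives no sample size, event count or power for PFS, so there is no figure to reproduce. The check has a textual part and an illustrative part.

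**Does anything in the text prevent the event?**

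- *Eligibility.* Category 3 requires that no chemotherapy be intended within six months. Category 1 carries no such condition for any drug, so an intended first-line start is compatible with entry.
- *Concomitant therapy.* Section 5.1.5 asks for a documented reason, but its last category is open-ended. Untreated mCRPC with progression documented at entry can satisfy it.
- *Early-event guard.* Bone-scan progression counts only on scans more than 12 weeks after randomisation. The therapy component has no such guard.
- *Stratification.* Untreated men share a stratum with men stable on therapy. A separate stratum would still count the starts as events.
- *The progression list.* This is the one limit that would work, but the PFS sentence does not repeat it.

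Men already on therapy for under four weeks at entry began before randomisation, so that start cannot be a PFS event for them.

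**How far could the hazard ratio move?** All inputs below are assumptions except where a section is named.

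- True progression hazard ratio 0.78 (the overall survival value in Section 12.2, borrowed because none is given for PFS).
- Control median time to true progression 16 months, so λ = ln 2 / 16 = 0.0433 per month.
- Intended first-line start exponential with mean 2 months in both arms, so μ = 1/2 = 0.5 per month.
- A share q of all men affected; 866 men; follow-up 36 to 72 months (36 months' accrual plus at least 36 months' follow-up, Section 12.2).

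Among affected men the first-event hazard ratio is (0.78λ + μ)/(λ + μ) = (0.0338 + 0.5)/(0.0433 + 0.5) = 0.98. In the control arm the start comes first for μ/(λ + μ) = 0.5/0.5433 = 92% of them. Over other assumed values (median progression 12–24 months, median start 1–12 months) the ratio in affected men is 0.89–0.99 and the share is 50–96%.

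For the whole trial I simulated both groups together and fitted an unstratified Cox model. I ran it first without deaths, then with PFS censored at death as Section 12.5 prescribes. Deaths used the Section 12.2 control median of 33.5 months and hazard ratio 0.78, and were taken as independent of progression.

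| Share affected, q | PFS hazard ratio, no deaths | PFS hazard ratio, censored at death |
|---|---|---|
| 0% | 0.78 | 0.78 |
| 10% | 0.80 | 0.81 |
| 20% | 0.82 | 0.83 |
| 30% | 0.84 | 0.85 |
| 40% | 0.86 | 0.88 |

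Power at two-sided 0.05 falls from a little over 90% (about 746 events) at q = 0 to about 55% at q = 40% without deaths. With censoring at death it falls from about 83% (about 552 events) to about 40%. A separate calculation with an 18-month median to progression and median start of 2 to 6 months gives 0.82 at 20% and 0.85–0.86 at 40%.

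**The case against.** The best defence is that Section 11.1 already contains the limit. The therapy component of the PFS sentence is labelled clinical progression, which points back to the list, and the list requires the indication to develop after randomisation. Section 12.5 also refers to Section 11 as a whole. On that reading a drug chosen before consent is not an event. This reading is available and may be what was intended. What stands against it is that the sentence actually defining PFS counts the start itself and does not ask whether the indication is new.

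A reader might go further and infer that category 1 men are all due to begin planned treatment, so that their PFS merely dates standard care and Section 2.2 cannot be answered for them. The documents do not support that. They say only that these men have not started approved therapy. Some are already in their first four weeks of it. PFS is a composite, so a first-line start matters only when it precedes scan progression and a skeletal event.

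A reader might also infer a bias in favour of exercise, because switches for intolerance count as events and Section 1.1 says that "exercise may decrease fatigue and increase adherence to treatment regimens". That passage states a possibility, and no figure is offered. Such a bias would run in the opposite direction to the dilution. It justifies a sensitivity analysis and no firmer claim.

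Finally, the sizes above rest on assumed inputs, and the plan sets no power target for PFS. That is correct. They show direction and plausible scale only.

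**Conclusion.** The concern holds in a limited form. Section 11.1 is internally inconsistent, and under its PFS sentence an untreated man can have an event from a first-line start already indicated or intended at randomisation. Nothing in Sections 3.1, 4.5 or 5.1.5 rules this out.

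The expected effect is attenuation: from 0.78 to about 0.82–0.83 with 20% of men affected and 0.86–0.88 with 40%, under the stated assumptions. This supposes that the timing of such starts does not depend on arm. That is reasonable for plans fixed before allocation, but the trial is unblinded and it is not guaranteed. The share of untreated men and the timing of their treatment are not given, so the actual size cannot be determined.

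Overall survival is unaffected. This is a should-fix for a secondary endpoint and no threat to the primary analysis.

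**What to change.** Make the two statements in Section 11.1 agree, and carry the result into Section 12.5:

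- Before randomisation, record any mCRPC therapy already intended or indicated.
- State that starting that recorded therapy is not a PFS event unless scan progression or a skeletal event was documented after randomisation and before the start (in which case PFS has already ended at that earlier date). Otherwise the man stays at risk.
- All other new mCRPC therapy starts continue to count.
- Add two sensitivity analyses: (i) the present rule, counting every start; (ii) only starts whose recorded reason is progression, which leaves out, for example, switches for intolerance. Version (ii) should not be the main definition, because it replaces a dated event with an unblinded judgement of the reason.

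The cost is wording, one baseline field and somewhat fewer PFS events. Section 5.1.5 already captures therapy dates and reasons, but only until 28 days after Cycle 24, so analysis (ii) needs the reason added to the twice-yearly follow-up. For any men already randomised, the field can be completed only from records dated before randomisation. The change concerns how events are counted and alters nothing in patients' care.
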